The primary objective of the study is to evaluate the feasibility and efficacy of the new medical device in treatment of paediatric patients with forearm fractures. The key variables in this assessment are the evaluation of the functional and clinical outcome by measuring range of motion in forearm, wrist and elbow (e.g. measuring supination/pronation and flexion-extension movements), and subjective pain assessment during recovery. The primary objective will be met if these outcomes in the treatment group are at least comparable to those of the patients treated with standard of care (TEN nail), interpreted by using the Price's classification system (<15 degrees of change in motion range is excellent clinical outcomes), and Flynn's criteria for upper extremity assessment (<10 degrees of change in motion range justifies satisfactory outcomes). The potential difference less than 10 degrees are to be determined not clinically significant. The raw results of clinical measurements and statistical significance of each finding are to be reported.

Secondary Objectives

The secondary objectives of the study are to evaluate the radiographic outcome of the forearm fracture treatment in patients treated using the study device. The key variables in assessment of these objectives are:

- fracture reduction and angulation,
- formation of bridging callus and consolidation (union, delayed union, non-union and malunion)

The method in assessment of key variables is plain radiographic evaluation. The secondary objective will be met if these outcomes in the treatment group are at least comparable to those of the patients treated with standard of care (TEN nail). According to the previous literature, angular deformity of <10 degrees in radius and/or ulna is to be determined not clinically significant [27-29].

Soft-tissue reaction against the biodegradable implant are to be studied by Magnetic Resonance Imaging (MRI) for a randomly selected sub-group of at least 10 patients.

Design of the Clinical Investigation

Type and Design of The Study

This is a randomized parallel-group **two-centre** study on the use of bioabsorbable intramedullary nail device for fixation of the radial and ulnar shaft fractures in children. All patients will receive the standard of care for other injuries caused by the trauma.

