1.1.11 Primary Performance Variable

Evaluation of functional and clinical outcome consists of following determinations:

Clinical Investigation Plan

Bioabsorbable Intramedullary Nail Fixation of Forearm Fractures in Children

- Measurements of the range of motion (ROM) in the forearm, expressed as degrees \pm SD
 - Loss of supination and pronation of the forearm (graded according to the table below),
 - Loss of flexion and extension of elbow and
 - Loss of dorsiflexion and palmar flexion of the wrist, graded according to the Flynn's criteria (<10 degrees of change are excellent or good i.e. satisfactory; >10 degrees of change are fair or poor i.e. unsatisfactory); and Price's classification.
- General pain and pain at fracture site assessed by VAS, expressed as mm \pm SD
 - Duration of post-operative medication for pain

Table 1 Classification of outcome, graded using a system described by Price [25]

Outcome	Loss of Forearm Rotation and Symptoms
Excellent	$\leq 15^\circ$ loss of forearm rotation and no complaints with strenuous activity
Good	A loss of forearm rotation of 15° to 30° and only mild complaints with strenuous physical activity
Fair	A loss of forearm rotation of 30° to 90° and mild complaints during activities of daily living
Poor	All other outcomes

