1.1.14 Other Variables

Other variables documented in CRF are:

- Operation time
- Number of days lost from usual activities
 - Parents lost working days
- Length of hospitalization stay
- Complaints in daily living
- Esthetics

Statistics

Recommended statistical methods will be applied. All deviations made after approval of the CIP will be described and justified in the final study report.

Sample Size Considerations

Primary outcome variable in this study is loss of supination and pronation within 6, 12, 26, 52, and 104 weeks after surgery. The non-inferiority margin is set to be 80 % in the calculations (=Power).

It is previously known that the forearm pronation in this age group is 81.2 degrees (95% CI 79.6-82.28) and 79.6 degrees (95% CI 78.8-80.4) in girls and boys, respectively. The corresponding supination archs are 90.0 degrees (95% CI 88.0-92.0) and 87.8 degrees (95% CI 85.7-89.9). [26] The standard deviation (SD) is 6.1 degrees in pronation and 7.6 degrees in supination. We determined that the new method (ActivaNail –intramedullary fixation) should

Clinical Investigation Plan

Bioabsorbable Intramedullary Nail Fixation of Forearm Fractures in Children

result to the forearm rotational range of motion that is not more than 15 degrees lower, compared to the rotational range of motion in TEN group, according to the Price's classification (<15 degrees of decrease refers to excellent outcome).

Difference between means in the groups is set as 7.0 and the Alpha as 0.05. The sample size is estimated to be 13 experimental subjects and 13 controls according to an unpaired two sample Student t test. This study population will also be exclusively large enough to recognize decrease in the ROM that is clinically significant (>15 degrees of decrease in supination or pronation in ActivaNail compared to TEN group).

Statistical Hypothesis

The following hypothesis will be tested for the primary efficacy variable:

H₀: Investigational device is inferior to comparative devices

H₁: Investigational device is non-inferior to comparative devices

The non-inferiority limit is set to 80 %. Thus, non-inferiority is shown if the upper limit of the 95% confidence interval for the difference is less than or equal to 5 %.

Statistical Methods

All operated subjects who reach the 2-year follow-up will be included in the statistical analysis. Study data will be tabulated by treatment groups with descriptive summary statistics.

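### The non-inferiority rule in section 10.2 cannot be applied as written: its 80 % is the power, its 5 % has no base, and the primary variable is in degrees

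*Protocol*

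**What the plan says.** - **10.1 Sample Size Considerations** introduces the figure: "The non-inferiority margin is set to be 80 % in the calculations (=Power").
- **10.2 Statistical Hypothesis** reuses it: "The non-inferiority limit is set to 80" %. The next sentence opens with a word of inference and gives the decision rule: "non-inferiority is shown if the upper limit of the 95% confidence interval for the difference is less than or equal to 5" %.
- **Primary variable.** 10.1 names loss of supination and pronation. Section 9.6 (1.1.11, Primary Performance Variable) gives the unit: "Measurements of the range of motion (ROM) in the forearm, expressed as degrees". Under 10.3 the treatment difference and its 95% confidence interval come from a repeated-measures analysis of variance.
- **Figures in degrees outside 10.2.** 10.1 asks for "the forearm rotational range of motion that is not more than 15 degrees lower" than in the TEN group, and describes as clinically significant ">15 degrees of decrease in supination or pronation in ActivaNail compared to TEN group". Section 8.1 says: "The potential difference less than 10 degrees are to be determined not clinically significant".
- **Sizing input.** "Difference between means in the groups is set as 7.0 and the Alpha as 0.05", which leads to 13 per group by an unpaired t test.

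**The concern.** Sections 10.1 and 10.2 treat a power as a margin, then move from 80 % to 5 % with no step between them and no statement of what the 5 % is a percentage of. The interval to be judged is in degrees, so the comparison that 10.2 asks for cannot be made.

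This is the only formal success rule for the primary hypothesis. An analyst would have to substitute a limit, and the protocol offers several. The 10-degree and 15-degree statements do not contradict each other, but they leave 10 to 15 degrees unclassified, and no sentence makes either figure the limit in 10.2. The study is unblinded (9.1). If the limit is settled once results are known, the results can steer the conclusion.

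**Working it through.** **Step 1: reproduce the plan's own sample size.** Inputs from 10.1 and 10.3: difference 7.0, pronation SD 6.1, alpha 0.05, two-sided, unpaired t test. Power comes from the non-central t distribution with 2n − 2 degrees of freedom and non-centrality 7.0 / (6.1 × √(2/n)).

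- n = 12 per group: 76.6%
- n = 13 per group: 80.1%

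So 13 is the smallest size that reaches 80%, and the 80 % works as power. No arithmetic leads from 80 to 5: the complement of 80 % is 20 %, and the only 5 % nearby is alpha.

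**Step 2: what 13 per group can resolve.** This is an illustration only. It uses a single-time-point t analysis (the plan is a repeated-measures model) and assumes that the protocol's SDs, quoted with reference ranges of motion, apply to loss after fracture.

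Half-width of the 95% interval = t(0.975, 24) × SD × √(2/13) = 2.064 × SD × 0.3922

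- Pronation, SD 6.1: 4.94 degrees
- Supination, SD 7.6: 6.15 degrees

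**Step 3: compare three readings of the limit.** For 5 % of a single reference arc, I average the girls' and boys' means in 10.1:

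- Pronation: (81.2 + 79.6)/2 = 80.4, and 5 % is 4.02 degrees
- Supination: (90.0 + 87.8)/2 = 88.9, and 5 % is 4.45 degrees

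The largest observed deficit that passes is the limit minus the half-width. Power is at a true difference of 0, 13 per group.

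| Reading of the limit | Largest passing observed deficit, pronation / supination (degrees) | Power, pronation / supination |
|---|---|---|
| 15 degrees | 10.06 / 8.85 | >99.9% / 99.8% |
| 10 degrees | 5.06 / 3.85 | 98.0% / 89.6% |
| 5 % of a single arc | −0.92 / −1.71 | 36% / 30% |

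Two results show the effect:

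- Observed extra loss of 7 degrees: upper limit 7 + 4.94 = 11.94 or 7 + 6.15 = 13.15. It passes at 15 and fails at 10.
- Observed difference of 0: upper limit 4.94 or 6.15. It passes at 10 and 15 and fails at 5 % of a single arc.

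Across these readings the verdict is open for observed differences from −0.9 to 10.1 degrees (pronation) or −1.7 to 8.8 degrees (supination). Outside those ranges all three agree.

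**Step 4: other bases and SDs.**

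- 5 % of summed rotation: 0.05 × 169.3 = 8.47 degrees. If the arcs are independent, the SD is √(6.1² + 7.6²) = 9.745 and the half-width 7.89, so an observed deficit up to 0.58 would pass.
- If the SD of loss were 10 to 15 degrees (an assumed range), the half-width is 8.1 to 12.1. Power at a true difference of 0 is then 96% to 69% at 15 degrees and 69% to 37% at 10 degrees.
- Whatever the SD, the 10- and 15-degree readings disagree over a band of 15 − 10 = 5 degrees of observed difference.

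**The case against.** The best defence is that the intended margin is on the page. Section 10.1 states a limit of 15 degrees against TEN and ties it to the Price classification. On this view 10.2 merely failed to carry it over. The 10-degree figure is then the weaker rival: it follows directly on Flynn's criteria, which section 9.5 (1.1.9) describes as an elbow assessment, while forearm rotation is graded by the Price table. This makes 15 a plausible candidate, but it does not rescue the rule. Section 10.2 never refers to 15, the sizing uses 7.0, and the 10-degree sentence in 8.1 follows a comparison of the treatment group with TEN that covers the forearm. If 15 was meant, 10.2 still needs the same correction.

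Other points:

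- **7.0 is a further candidate.** As a margin at a true difference of 0 with SD 6.1, it also gives 80.1% power. That stands, and it adds one more open reading. The open ranges above hold only for the three readings compared.
- **A percentage would suit a difference in proportions of Price or Flynn grades.** The sizing is a t test on means and the analysis is a model for a continuous variable. No proportion is attached to the hypothesis.
- **Section 8.1 has its own success criterion.** Requiring outcomes at least comparable to TEN is a stated aim, but not a confidence-interval rule.
- **A statistical analysis plan may define the margin, and section 10 requires deviations to be justified.** The protocol states a rule here and states it wrongly, so a later plan could only replace it. A deviation clause needs a readable rule to deviate from.

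**Conclusion.** The concern holds and must be fixed. That 80 % is the power, that the 5 % has no stated base or derivation, and that variable and interval are in degrees all follow from the text and depend on no assumption.

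The size does rest on assumptions: one time point, 13 per group, and the protocol's SDs. Under these, the reading chosen moves the power at no true difference from about 30% to over 99%, and reverses the verdict over roughly 11 degrees of observed difference (10.06 + 0.92 = 10.98 for pronation; 8.85 + 1.71 = 10.56 for supination). The absolute power figures would shift with another SD. The 5-degree band of disagreement between 10 and 15 would not.

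**What to change.** Before any outcome data are seen:

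1. In 10.1, describe 80 % as power only.
2. Replace the last two sentences of 10.2 with a rule of this form: *Non-inferiority is shown if the upper limit of the two-sided 95% confidence interval for the difference in mean loss of [pronation / supination / total forearm rotation] at [time point] (bioabsorbable minus TEN, from the model in 10.3) is at most [M] degrees.* If both arcs are tested, add that both must pass.
3. State the time point. 10.1 lists 6, 12, 26, 52 and 104 weeks. The synopsis and 10.3 point to two years. Table 2 measures motion at 4, 12, 26 and 104 weeks only.
4. The sponsor chooses and justifies M, and reconciles the statements in 8.1 and 10.1 with it. No value is preferred here.
5. State what 7.0 represents, and restate the power that 13 per group gives for the chosen variable and M.

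**Cost:** edits to 10.1 and 10.2 and one reconciling sentence in 8.1. The correction does not itself require more patients, but the restated power may differ from 80%. For example, with the protocol's SDs and M at 5 % of a single arc, 80% power would need 38 (pronation) or 47 (supination) per group, so the sponsor should see the power before settling M.

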35 subjects will be enrolled at the University Hospital of Oulu and Central Hospital of Päijät-Häme to appreciate the potential drop-outs. The minimum number of patients in both groups (study implant vs. titanium implant) is 13. To minimize any selection bias, the patients will be sequentially randomized into these groups.

The study cannot be executed in a blinded fashion, because the orthopaedic surgeon and the operating room staff will inevitably be aware of the type of the implanted device. The patient must be also informed if the signed implant needs removal: the titanium alloy devices will be removed at 6 months, while the absorbable device will not require removal surgery.

Selection of the Study Population and Enrollment

The study begins with the signing and dating of the informed consent. All subjects and/or guardian must provide informed consent. During the consent procedure, the person obtaining consent must inform the subject of all elements of informed consent. Adequate time must be allowed for the subject to ask questions and make a voluntary decision. No protocol-specific procedures, including screening procedures, are performed until the subject has signed and dated the independent ethics committee approved informed consent form. Subjects must also meet the inclusion and exclusion criteria to be enrolled in the study. The participation in this clinical investigation is voluntary and the subject may interrupt the participation at any time, which is to be clearly informed.

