1.1.7 Visit Schedule

For each subject, the study consists of assessments preoperatively, immediately after operation and the follow up visits postoperatively. The recommend time window of scheduled visits is ± 7 days. The clinical assessments and procedures performed at each visit are shown in Table 2.

Clinical Investigation Plan

Bioabsorbable Intramedullary Nail Fixation of Forearm Fractures in Children

During these visits will be investigated: function of both arms, radiological fracture healing, well-being and incidence of complications.

Table 2 Assessment and procedures at each visit

Assessment	Operation		4 week	12 weeks	26 weeks	52 weeks	104 weeks
	Pre-operative	Post-operative					
	Visit 1	Visit 2	Visit 3	Visit 4	Visit 5	Call 6	Visit 7
Informed consent, inclusion and exclusion criteria	X						
Demographics, medical history	X						
Injuries and comorbidities	X						
Randomization	X						
Fracture reduction and fixation	X						
Cast removal			X				
TEN nail removal					X		
Primary performance variable	Operation		4 week	12 weeks	26 weeks	52 weeks	104 weeks
	Pre-operative	Post-operative					
	Visit 1	Visit 2	Visit 3	Visit 4	Visit 5	Call 6	Visit 7
Functional and clinical outcome evaluated by measuring rate of motion			X	X	X		X
Pain assessment		X	X	X	X	X	X
Subjective		X	X	X	X	X	X

Clinical Investigation Plan

Bioabsorbable Intramedullary Nail Fixation of Forearm Fractures in Children

result							
Secondary variables	Operation		4 week	12 weeks	26 weeks	52 weeks	104 weeks
	Pre-operative	Post-operative					
	Visit 1	Visit 2	Visit 3	Visit 4	Visit 5	Call 6	Visit 7
Radiographic outcome and bone union formation evaluated by plain radiographs	X	X	X	X	X		X
Radiographic outcome and bone union formation evaluated by MRI imaging		X*		X*		X*	X*
Safety and tolerability variables	Operation		4 week	12 weeks	26 weeks	52 weeks	104 weeks
	Pre-operative	Post-operative					
	Visit 1	Visit 2	Visit 3	Visit 4	Visit 5	Call 6	Visit 7
Adverse events	X	X	X	X	X	X	X
Concomitant medications	X	X	X	X	X	X	X
Conclusion of participation							X

* Radiographic outcome and bone union formation of 5-10 subjects will be evaluated by MRI imaging immediately after operation and three follow up visits

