1.1.13 Safety Variables

Incidence of adverse events (AE) and serious adverse event (SAE) will be expressed as proportion per group. These consist of e.g. complications related to injury or treatment and will be separated into resolved versus long-term or non-resolved complications, which included a need for return to the operating room. Monitored AE's are:

Clinical Investigation Plan

Bioabsorbable Intramedullary Nail Fixation of Forearm Fractures in Children

- Fracture delayed union, nonunion and malunion
- Incidence of infection
- Intra-operative complications related to fixation hardware
- Need for secondary reduction due to fracture instability
- Osteolysis
- Biocompatibility reactions
- Mechanical implant failure

The potential drop-outs by any reason are recognized and reported, despite the lack of 2-year follow-up data, whilst no comparisons at end-point are available.

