The study data of the CRFs will be stored at the research sites and copies without personal identification data will be sent to the sponsor for storing.

Clinical Investigation Plan

Bioabsorbable Intramedullary Nail Fixation of Forearm Fractures in Children

Quality Assurance

Bioretec has a certified Quality Management System according to ISO 13485:2003. Investigational devices will be tested according to SOP's of the Bioretec Ltd using the test equipment maintained and calibrated according to relevant SOP's of Bioretec Ltd.

Discontinuation and Withdrawal of Subjects

A subject may be discontinued (withdrawn) from the study at any time if the subject or the investigator believes it is not in the best interest of the subject to continue participation in the study. Subjects withdrawn from the study will not be replaced, regardless of the reason for withdrawal. All study data provided up to the time of withdrawal will be collected and reported. This information will be recorded in the subject's source documentation and in the CRF. Subjects who discontinue their participation or are withdrawn from the trial will be asked to participate in a final study visit at 104-week follow-up visit.

Termination of the Study

The sponsor may terminate individual subject or group of subjects, or the entire investigation, at any time for any of the following reasons:

- Failure to enrol subjects
- Protocol violations
- Inaccurate or incomplete data
- Unsafe or unethical practices
- Questionable safety of the test device
- Suspected lack of efficacy of the test device
- Administrative decision.

If the investigator terminates the study prematurely, the investigator provides the ethical committee and the sponsor with a written statement describing why the study was terminated prematurely. Prompt compliance with this requirement is essential so that the sponsor may comply with its regulatory obligations.

Clinical Investigation Plan

Bioabsorbable Intramedullary Nail Fixation of Forearm Fractures in Children

CIP Amendments and Deviations

All amendments to the CIP with the justifications will be agreed and recorded between sponsor and the principal investigator. Any deviation to this clinical investigation plan made by investigators shall be recorded with an explanation for deviation and reported to sponsor. The significance of deviation will be determined by sponsor. When appropriate, Ethical Committee and other appropriate regulatory bodies are informed.

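### Section 10.3 analyses operated children who reach 2 years and leaves drop-outs out of the end-point comparison; if outcome-related loss differs by arm, the non-inferiority comparison is biased, in either direction

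*Protocol*

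**What the plan says.** - **Analysis set.** Section 10.3: "All operated subjects who reach the 2-year follow-up will be included in the statistical analysis". Section 1.1.13 says that drop-outs are reported "despite the lack of 2-year follow-up data, whilst no comparisons at end-point are available". The protocol defines no all-randomised or all-operated comparison.
- **Primary variable and model.** Section 10.1: "Primary outcome variable in this study is loss of supination and pronation within 6, 12, 26, 52, and 104 weeks after surgery". Section 10.3 plans a repeated-measures analysis of variance.
- **Data on file.** In Table 2 the row "Functional and clinical outcome evaluated by measuring rate of motion" is marked at weeks 4, 12, 26 and 104; week 52 is a call without this measurement. These weeks differ from those in section 10.1. Section 13 adds: "All study data provided up to the time of withdrawal will be collected and reported".
- **Withdrawal.** Section 13 lets the investigator withdraw a child on judgement and does not replace withdrawn children, but they "will be asked to participate in a final study visit at 104-week follow-up visit". Section 14 lets the sponsor terminate individual subjects, and suspected lack of efficacy of the test device is among the listed reasons.
- **Blinding and later care.** Section 9.1: "The study cannot be executed in a blinded fashion", and "the titanium alloy devices will be removed at 6 months, while the absorbable device will not require removal surgery".

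**The concern.** Randomisation makes the arms comparable at entry. A set defined by reaching 2 years keeps that comparability only if loss is unrelated to outcome, or related to it equally in both arms.

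The documents leave room for something else. Families and investigators know the implant, children can be withdrawn on judgement, and one listed termination reason concerns efficacy of the test device only. If poor results are lost mainly from the device arm, completers look too good and the bias runs toward non-inferiority. If they are lost mainly from the control arm, it runs against the device.

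The rule also sits badly with the planned model. By Table 2, a child lost after week 26 has three of four planned range-of-motion measurements, and none enters the comparison. With arms this small, one or two children move the mean by degrees.

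The point concerns the range-of-motion comparison. Complications and drop-outs are still reported.

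**Working it through.** **1. The plan's own figure.** Difference 7.0 degrees, SD 6.1 (pronation), two-sided alpha 0.05 and an unpaired t test give 13 per arm, with power of about 80%. That reproduces section 10.1. Enrolling 35 against 26 needed leaves 35 − 26 = 9 places (25.7%). This protects power; it does not protect against bias.

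**2. Size of the bias.** Let kD and kC be the failures lost in the device and control arms, n the number per arm, and E the extra loss of rotation in a failure. With no other device difference and all failures lost, completers show a difference of about 0, while the difference in all children is

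(kD − kC) / n × E.

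Assumed: n = 16 and E = 35 degrees (total loss 40, with an assumed mean loss of 5, which lies in the 30 to 90 degree Fair row of Table 1).

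- 1 v 0: 1/16 × 35 = 2.2 degrees
- 2 v 0: 2/16 × 35 = 4.4
- 3 v 0: 3/16 × 35 = 6.6
- The same losses in the control arm: −2.2, −4.4, −6.6
- Range over E for 1, 2 and 3 lost: 1.6, 3.1, 4.7 at E = 25; 3.8, 7.5, 11.3 at E = 60

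A hidden difference above 10 degrees needs 5 of 16 at E = 35 (10.9) or 3 of 16 at E = 60 (11.3).

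**3. Equal failures.** With 1 v 1 or 2 v 2 lost failures (E = 35, SD 6.1) the difference is unbiased. The mean 95% CI half-width is 4.5 and 4.7 degrees for completers, against 7.7 and 9.7 for all children. The completer interval is valid for completers but narrower.

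**4. Near the margin.** Suppose the true difference equals the margin (10 or 15 degrees), 18 and 17 are randomised, 4 are lost per arm, and only device-arm losses are outcome-related and 15 degrees worse. The bias is 4/18 × 15 = 3.3 degrees. Simulated non-inferiority is declared in 19–28% of trials (SD 7.6 to 6.1) instead of about 2.5%. In the mirror case it is 0.1% or less.

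**5. What a mixed model recovers.** Take 2 v 0 failures at E = 35 (true 4.4), lost after week 26. With equal correlation r between visits, the week-104 value regresses on each of three earlier visits with coefficient r/(1 + 2r).

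- r = 0.5: coefficient 0.25. A failure visible only at week 26 recovers 0.25 × 4.4 = 1.1 degrees.
- r = 0.7: coefficient 0.29. A failure visible at all three visits recovers about 0.875 × 4.4 = 3.9 degrees.

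Recovery is therefore partial, 25–88% under these assumptions.

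**6. Cost of the sensitivity analysis.** True difference 0, 16 per arm, mean loss 5, losses unrelated to outcome, 30 degrees assigned to each missing child, pooled t interval. Share of simulated trials showing non-inferiority at 10 degrees for 1, 2 and 3 losses per arm:

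| SD | Sensitivity analysis | Completers |
|---|---|---|
| 6.1 | 96%, 90%, 81% | 98–99% |
| 7.6 | 87%, 78%, 69% | 90–93% |
| 9.75 | 71%, 62%, 55% | 71–77% |

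SD 9.75 = √(6.1² + 7.6²) applies if the scale is the total arc and the two components are independent. At 15 degrees the sensitivity analysis passes in 95% or more throughout. The SDs in section 10.1 are reference values for motion, used here as an assumption for loss.

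**The case against.** **What stands.**
- The bias is conditional, and the protocol gives no drop-out rate or imbalance. The sizes above rest on assumptions, including that every failure is lost. The 104-week invitation works against that, and a failure or reoperation does not in itself exclude a child.
- The visit schedule is the same in both arms, and nail removal falls at the shared week-26 visit. Removal surgery is therefore a weak reason to expect different retention. Lack of blinding and the withdrawal and termination provisions are the better reasons, and they show possibility, not occurrence.
- Section 10.3 does not contain the word only. Section 1.1.13 makes that the natural reading.
- The Synopsis places the primary assessment at two years, which partly explains the completer set. It does not require earlier data to be discarded. A separate analysis plan might add other sets, but the protocol itself fixes this one.

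**Stronger readings that the documents do not support.**
- A reader might infer that the trial will wrongly declare non-inferiority. At 35 degrees, 1 to 3 lost failures hide less than 10 degrees. False declarations need a true difference already near the margin, or more or worse losses.
- A reader might treat 13 children per arm as a floor that caps the losses. Section 1.1.3 speaks of 13 enrolled and treated, section 13 does not replace withdrawals, and no allocation ratio is stated. The protocol sets no bound on losses.
- Table 1 grades total forearm rotation, while the SDs are for single components. Using the single-component SDs alone understates the cost of the sensitivity analysis, hence the third row in the table.

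**Conclusion.** The point holds in conditional form and should be fixed. The protocol ties the range-of-motion comparison to a post-randomisation event and leaves usable earlier data out of it. If outcome-related loss differs by arm, the difference is biased, in either direction; if it is equal, the difference is unbiased but the completer interval understates the uncertainty for all children.

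On assumed values (16 per arm, lost failures 35 degrees worse, all of them lost), 1 to 3 lost failures in one arm hide 2.2 to 6.6 degrees. The upper end is close to the 7.0-degree planning difference but below the 10 and 15 degree thresholds. Neither a loss rate nor a limit on losses can be taken from the protocol, so this shows sensitivity and is not a forecast.

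**What to change.** 1. In section 10.3, state that all randomised subjects, excluding pilot patients, are analysed in the group to which they were randomised. List any who were randomised but not operated, with reasons.
2. Replace the analysis-of-variance sentence in section 10.3 with a mixed model for repeated measures that uses all available visits, with the 2-year treatment difference as the primary contrast. Keep the 2-year completer set as supportive. Align the visit weeks in section 10.1 with Table 2.
3. Add one sensitivity analysis that gives children with no 2-year value a single unfavourable rotation-loss value. It must be on the scale of the primary variable and fixed before any comparison by group: 30 degrees if that scale is total forearm rotation, the lower bound of Fair in Table 1. Keep all observed 2-year values, including those after reoperation.

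**Cost.** Wording and one extra analysis; no new visits or data. The mixed model assumes data missing at random and removes only part of the bias. Children lost before the first range-of-motion visit contribute only through the sensitivity analysis. That analysis is harder to pass (step 6), most of all at 10 degrees and on the total-arc scale. A value of 30 is also milder than the failure assumed above: with 2 v 0 losses it returns (30 − 5) × 2/16 = 3.1 of the 4.4 degrees.
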